4.4. Multiple Assessments for the Same Assessment Time Point

In the case of multiple observations at a specific visit, the first non-missing measurement will be used for analysis, unless multiple study assessments are expected (e.g., pre-dose vs post-dose). When multiple study assessments are expected, the first non-missing measurement for the visit and assessment time point will be used for analysis.

4.5. Multiple Study Centers

No adjustment for study center is planned.

4.6. Covariate Adjustment in Primary Analysis

No covariate adjustment will be made.

4.7. Sample Size Reassessment

Not applicable.

4.8. Interim Analyses

In this Simon's two-stage design, 28 efficacy evaluable patients will be enrolled in the first stage. If 9 or fewer patients have achieved a confirmed response (CR or PR), the study will be terminated for futility. Enrollment will not be halted for this futility analysis.

4.9. Timing of Primary Analysis of ORR

To allow for reasonable duration on treatment to achieve a confirmed response, the primary analysis for ORR will be conducted after all efficacy evaluable patients have:

- undergone at least 6 post-baseline tumor assessments, or
- experienced radiological disease progression, or

- died or had clinical progression within 105 days of first dose of MIRV, or
- withdrawn from study for other reasons.

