3.2. Study Overview

This Phase 2 study is designed to evaluate the efficacy and safety of MIRV in patients with recurrent platinum-sensitive, high-grade serous epithelial ovarian cancer, primary peritoneal, or fallopian tube cancer (EOC), whose tumors express a high level of FR α , referred to throughout as rPSOC (recurrent platinum-sensitive ovarian cancer). Patients will have had at least 2 prior lines of therapy. These will include at least 2 lines of platinum-containing therapy or 1 line with a documented platinum allergy. All patients will be, in the opinion of the Investigator, appropriate for non-platinum single-agent therapy for their next line of therapy. FR α positivity will be defined by the Ventana FOLR1 (FOLR1-2.1) CDx assay (Ventana FOLR1 Assay)..

Eligible patients will receive MIRV 6mg/kg AIBW Q3W until disease progression, unacceptable toxicity, withdrawal of consent, death, or until the Sponsor terminates the study (whichever comes first).

Tumor assessments, including radiological assessments by CT/MRI scans will be performed at Screening and subsequently every 6 (± 1) weeks from C1D1 for the first 36 weeks then every 12 (± 3) weeks until disease progression, death, the initiation of subsequent anticancer therapy, or patient's withdrawal of consent, whichever occurs first. CT/MRI scans will be collected for sensitivity analysis by blinded independent central review (BICR)

Patients who discontinue MIRV for reasons other than PD will continue with tumor assessments until documentation of PD or the start of a new anticancer therapy, whichever comes first. Prior to Week 36 (from C1D1), assessments should occur every 6 weeks (± 1 week) as allowed by local requirements but must occur at an interval of no more than 12 weeks. After Week 36, assessments will occur every 12 weeks (± 3 weeks) until documentation of PD per RECIST v1.1 ([Eisenhauer 2009](#)) or the start of new anticancer therapy.

All patients who discontinue MIRV will be followed for survival every 3 months (± 1 month) until death, lost to follow-up, withdrawal of consent for survival follow-up, or End of Study (EOS) (whichever comes first). Additional survival follow-up calls may occur periodically, if needed.

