3.2.2. Power and Sample Size

The primary endpoint of this study is ORR as assessed by the Investigator. The study is designed to test the null hypothesis that the ORR is $\leq 28\%$ using an optimal Simon's two-stage design ([Simon 1989](#)) without a planned pause in enrollment given preliminary efficacy and established safety of MIRV.

The optimal two-stage design to test the null hypothesis that the ORR is $\leq 28\%$ versus the alternative that the ORR is $\geq 48\%$ has an expected sample size of 37.74 and a probability of early termination of 0.762. If the ORR is $\leq 28\%$, there is a 0.024 probability of rejecting the null hypothesis (the target 1-sided alpha value was 0.025). If the ORR is $\geq 48\%$, there is a 0.9

probability of rejecting the null hypothesis. After testing the drug on 28 efficacy evaluable patients in the first stage, the study will be terminated for futility if 9 or fewer respond. If the study goes on to the second stage, a total of 69 efficacy evaluable patients will be enrolled. If the total number responding is more than 26, the null hypothesis is rejected.

Approximately 75 patients will be enrolled so that a total of 69 patients will be efficacy evaluable.

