6.1. Efficacy Outcomes

6.1.1. Best Overall Response

Best overall response (BOR) for a patient is the best response designation as assessed by the Investigator recorded between the date of first dose of MIRV and the date of objectively documented PD per RECIST Version 1.1, the date of the start of new anti-cancer therapy, or the date of study discontinuation, whichever occurs first. When an analysis cutoff date is implemented, only radiological assessments occurring on or prior to the cutoff date will be used for analysis. Patients with an overall response of CR or PR must have a repeat tumor assessment performed no less than 4 weeks (28 days) after the criteria for response are first met. When stable disease is the best overall response, it must meet the minimum duration of 35 days (6 weeks – 1 week window = 35 days from the date of first dose of MIRV). The confirmatory scan is valid following treatment discontinuation if the patient has not started a new anti-cancer therapy. Once

a patient has a confirmed response, tumor response may only be recorded as continued response or progressive disease.

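### SAP 4.9 has no trigger condition for a patient who starts new therapy before scan 6 without progression, and it can be met while a first response at scan 6 is still unconfirmed

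*SAP*

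**What the plan says.** SAP 4.9 gives four alternatives, and every efficacy evaluable patient must meet one of them before the primary ORR analysis:

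1. she has "undergone at least 6 post-baseline tumor assessments";
2. she has had radiological progression;
3. she "died or had clinical progression within 105 days of first dose of MIRV";
4. she has left the study for another reason.

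The stated purpose is to allow enough time on treatment for a response to be confirmed. Protocol 10.3.1.1 has the same list with four scans in condition 1. SAP section 9 declares the change to six.

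Three other rules bear on this list:

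- **Scanning off treatment.** Under SAP 3.2, patients without PD who stop MIRV "will continue with tumor assessments until documentation of PD or the start of a new anticancer therapy, whichever comes first". Protocol 9.3.3 keeps patients in survival follow-up after new therapy starts. The reasons for leaving the study in Protocol 5.6.2 do not include new therapy.
- **Response.** Under SAP 6.1.1, a response needs confirmation: the patient "must have a repeat tumor assessment performed no less than 4 weeks (28 days) after the criteria for response are first met". The window for best overall response closes at the earliest of PD, new therapy or study discontinuation, and scans after an analysis cutoff are not used.
- **End of study.** Protocol 12.8 sets it 12 months after the primary ORR analysis.

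**The concern.** The trigger fixes the date of the primary analysis, of the initial DOR analysis and, 12 months later, of the DOR update and the end of the study. It should therefore be reachable by every kind of patient the plan expects, and it should not be met while a patient's primary outcome is still open.

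It falls short on both counts. A patient who changes therapy before progression is foreseeable: the DOR and PFS censoring rules in SAP 6.1.1.2 and 6.1.2 provide for her. The trigger does not. In the other direction, condition 1 counts scans and does not ask whether a response seen on the last of them has been confirmed. The consequences are an unclear analysis date in the first case and a possible undercount of responders in the second.

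**Working it through.** **Inputs.** SAP 3.2.2: null ORR 28%, alternative 48%; 28 patients in stage 1, where "the study will be terminated for futility if 9 or fewer respond"; 69 patients in all, with rejection above 26 responders. SAP 3.2: scans every 6 (±1) weeks to Week 36, then every 12 (±3) weeks. SAP 6.1.1: repeat scan at least 28 days after the first response.

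**The plan's own figures.** The SAP says the design "has an expected sample size of 37.74 and a probability of early termination of 0.762", with type I error 0.024 and power 0.9.

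- Early termination: P(X1 ≤ 9 | 28, 0.28) = 0.7624.
- Expected sample size: 28 + (1 − 0.7624) × 41 = 37.74.
- P(reject | p) = Σ over x from 10 to 28 of P(X1 = x | 28, p) × P(X2 > 26 − x | 41, p). This gives 0.0245 at 28% (0.02449 before rounding) and 0.9001 at 48%.

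All four figures are reproduced.

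**Which patients meet a condition.**

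| Patient, without radiological PD | Under SAP 4.9 |
|---|---|
| New therapy before scan 6, no clinical progression by Day 105, alive and in follow-up | None met |
| Clinical progression after Day 105, still being scanned | Can still meet 1 or 2 |
| Clinical progression after Day 105, then new therapy before scan 6 | None met |
| New therapy after scan 6, or after clinical progression by Day 105 | Already met |
| First CR or PR at scan 6 | Condition 1 met that day |

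The end of the study cannot release the patients who meet none, because it is itself timed from the primary analysis.

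**Length of the exposed period.** Scan k falls on Day 42k up to Week 36. With four scans the exposure ends at about Day 168 (Week 24). With six it ends at about Day 252 (Week 36; window Day 245 to 259), which is 84 days later. It starts at first dose and not at Day 105, because an early switch for a reason other than clinical progression is not covered either.

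**First response at scan 6.**

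- Earliest confirmation: Day 252 + 28 = Day 280 (Week 40).
- Next scheduled scan: Week 48, Day 336 (window Day 315 to 357).
- Nominal wait for that scan: 336 − 252 = 84 days, or 12 weeks.
- Longest wait within the windows: 357 − 245 = 112 days, or 16 weeks.

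Resolving a pending response therefore takes about 4 to 16 weeks.

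**Size.** One patient is 1/69 = 1.4 ORR points. For illustration, assume that k true responders are always lost at the final analysis and that stage 1 is unaffected. The final limit then becomes 26 + k:

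| k | Type I error at 28% | Power at 48% |
|---|---|---|
| 0 | 0.0245 | 0.900 |
| 1 | 0.0141 | 0.875 |
| 2 | 0.0077 | 0.838 |
| 3 | 0.0039 | 0.786 |

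These figures use the count rule of SAP 3.2.2. Under the Clopper-Pearson rule of SAP 4.10, 27/69 has a lower bound of 27.6% and fails, while 28/69 has 28.9% and passes. Starting from 28, the loss of one responder takes power from 0.875 to 0.838.

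**The case against.** Much can be said for the rule as it stands.

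- **Late clinical progression.** A reader might infer that anyone who progresses clinically after Day 105 can never satisfy the trigger. The documents do not support that: she stays under scanning until PD or new therapy and can meet condition 1 or 2. A patient scanned 12-weekly off treatment (Weeks 6, 12, 24, 36, 48, 60) also meets condition 1, only late.
- **Late death.** The 105-day limit may apply to clinical progression alone. Death is also a listed reason for leaving the study in Protocol 5.6.2, so condition 4 may cover it. The wording is ambiguous, but this is not a clear gap.
- **Bias.** A reader might infer that the uncovered patients distort ORR. They do not: their best overall response closed when new therapy began, so no choice of cutoff changes what they contribute.
- **Scan 6.** The trigger is a minimum. The last patient to qualify usually sets the date, so earlier enrollees will often have later scans by then. Any response still missed lowers ORR and type I error.
- **Four scans to six.** The change is declared and serves the stated purpose. It is not an error in itself.

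All of this stands. What remains is that no condition covers new therapy before scan 6. Stretching condition 4 to include it conflicts with Protocol 5.6.2 and 9.3.3. Nor does anything require the cutoff to wait for a pending confirmation.

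**Conclusion.** The point holds in a narrow form and is minor.

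First, a living patient who starts new anticancer therapy before scan 6, with no radiological PD and no clinical progression by Day 105, meets none of the four conditions. Read literally, one such patient holds the trigger open until she dies (if death counts under condition 4), withdraws or is lost. The harm is an uncertain analysis date, not a biased ORR.

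Second, a first response at scan 6 meets the trigger before it can be confirmed, and it counts as a non-response if the cutoff precedes the repeat scan. The cost is 1.4 points per patient, in the conservative direction. The fall in power from 0.900 to 0.875 rests on the assumption that exactly one true responder is lost. The documents give no expected number, and it may be zero.

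A reader might go further and infer that type I error is inflated, or that the whole decision turns on 26 versus 27 responders. The first is the reverse of what the calculation shows. The second describes only the count rule, since the confidence-interval rule turns on 27 versus 28.

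**What to change.** Amend SAP 4.9 as follows:

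- Add a condition: started new anticancer therapy.
- State that death at any time satisfies the trigger.
- Leave patients with late clinical progression who are still being scanned under conditions 1 and 2. Accepting clinical progression at any time would release patients whose response can still change.
- Add: any patient with an unconfirmed CR or PR at that time has had a repeat assessment at least 28 days later, or has had PD, died, started new anticancer therapy, withdrawn consent or been lost to follow-up. Withdrawal and loss must be included, or the added sentence would itself be open-ended.

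This is a change of wording with no new data collection, since survival follow-up already records the start of new therapy (Protocol Table 2, footnote s). The downside is that the cutoff may move by about 4 to 16 weeks if a scan-6 response is pending. The DOR update and the end of the study would move with it. If the cutoff has already been set, the study report should give its date, the number of patients who met no condition and the number of responses unconfirmed at that date.

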4.10. Test Sizes

For the primary endpoint of ORR, the null hypothesis that ORR is $\leq 28\%$ will be tested against 1-sided Type I error (α) of 0.025. This study will reject the null hypothesis if the lower bound of 95% (2-sided) confidence interval (CI) by the Clopper-Pearson method based for ORR is greater than 28%.

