10.1. Sample Size

The primary endpoint of this study is ORR as assessed by the Investigator. The study is designed to test the null hypothesis that the ORR is \leq 28% using an optimal Simon's two-stage design ([Simon 1989](#)) without a planned pause in enrollment given preliminary efficacy and established safety of MIRV.

The optimal two-stage design to test the null hypothesis that the ORR is \leq 28% versus the alternative that the ORR is \geq 48%, has an expected sample size of 37.74, and a probability of early termination of 0.762. If the ORR is \leq 28%, there is a 0.024 probability of rejecting the null hypothesis (the target 1 sided alpha value was 0.025). If the ORR is \geq 48%, there is a 0.9 probability of rejecting the null hypothesis. After testing the drug on 28 efficacy evaluable patients in the first stage, the study will be terminated for futility if 9 or fewer patients respond. If the study goes on to the second stage, a total of 69 efficacy evaluable patients will be enrolled. If the total number responding is more than 26, the null hypothesis is rejected.

Document ID: CLIN-00067	Title: IMGN853-0419 Clinical Study Protocol	Version: 2.0
Legacy ID: 26587		Approved Date: 12/22/202

Approximately 75 patients will be enrolled so that a total of 69 patients will be efficacy evaluable.

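### The SAP holds two success rules for the primary endpoint that disagree at 27 of 69 responders, and the stated 90% power belongs to only one of them

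*SAP*

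**What the plan says.** The design section sets up an optimal Simon two-stage test of "the null hypothesis that the ORR is \leq 28% versus the alternative that the ORR is \geq 48"% (Protocol 10.1, repeated in SAP 3.2.2). Stage 1 has 28 efficacy evaluable patients, and "the study will be terminated for futility if 9 or fewer respond". If the trial continues, 69 efficacy evaluable patients are enrolled in total, and if the "total number responding is more than 26, the null hypothesis is rejected". The stated properties are that "there is a 0.024 probability of rejecting the null hypothesis (the target 1-sided alpha value was 0.025"), that at a 48% response rate "there is a 0.9 probability of rejecting the null hypothesis", and that the design "has an expected sample size of 37.74 and a probability of early termination of 0.762".

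SAP 4.10 (Test Sizes) gives a different criterion for the same hypothesis. The study will "reject the null hypothesis if the lower bound of 95% (2-sided) confidence interval (CI) by the Clopper-Pearson method" is above 28%. SAP 4.11.1 adds that the primary hypothesis is tested through the confidence interval and that no p-value is reported.

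Protocol 10.3.1.1 mentions the Clopper-Pearson interval only for estimating the ORR. SAP section 9, which lists departures from the protocol, records the move from four to six post-baseline tumor assessments and nothing about the success rule. Neither document says which rule takes precedence.

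**The concern.** Both statements are written as decision rules for one null hypothesis, yet they rest on different sampling models. The Simon cut-off of 26 takes credit for the futility stop: some samples that would have reached 27 responders never get there because the trial ended at stage 1. That credit is what brings alpha below 0.025. A Clopper-Pearson interval treats the 69 patients as a single-stage sample and takes no such credit, so it should demand more responders.

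If so, a result exactly at the design's critical value could be called a success or a failure according to the section cited, and the choice could be made after seeing the data. The quoted power would also not be the power of the test in SAP 4.10.

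**Working it through.** **Inputs.** Null rate 0.28 and alternative 0.48; stage 1 of 28 patients, stopping at 9 or fewer responders; total 69, so 41 patients in stage 2; count rule rejects at 27 or more (all Protocol 10.1 and SAP 3.2.2). Interval rule: two-sided 95% Clopper-Pearson lower bound above 0.28 (SAP 4.10).

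**Step 1. Reproduce the stated design.** Let X1 ~ Bin(28, p) and X2 ~ Bin(41, p).

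- Probability of early termination under the null: P(X1 ≤ 9 | 0.28) = 0.7624 (stated 0.762).
- Expected sample size under the null: 28 + (1 − 0.7624) × 41 = 37.74 (stated 37.74).
- P(reject) = Σ over x1 = 10 to 28 of P(X1 = x1) × P(X2 ≥ 27 − x1). At p = 0.28 this is 0.0245 (stated 0.024); at p = 0.48 it is 0.9001 (stated 0.9).

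Every stated figure reproduces, for the count rule.

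**Step 2. Find the cut-off of the interval rule.** The lower bound for x responders of n is the 0.025 quantile of Beta(x, n − x + 1).

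| Responders of 69 | ORR | 95% Clopper-Pearson interval | Count rule | Interval rule |
|---|---|---|---|---|
| 26 | 37.7% | 26.3% to 50.2% | not rejected | not rejected |
| 27 | 39.1% | 27.6% to 51.6% | rejected | not rejected |
| 28 | 40.6% | 28.9% to 53.1% | rejected | rejected |

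The rules differ at 27 and at no other count when n = 69.

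**Step 3. Operating characteristics at n = 69.** The Step 1 formula applies, with 28 in place of 27 for the interval rule. The rows without the stop use a single binomial of 69.

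| Rule | Futility stop | Alpha at 28% | Power at 48% |
|---|---|---|---|
| Count, 27 or more | enforced | 0.0245 | 0.900 |
| Interval, 28 or more | enforced | 0.0141 | 0.875 |
| Count, 27 or more | not enforced | 0.0299 | 0.945 |
| Interval, 28 or more | not enforced | 0.0164 | 0.913 |

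With the stop enforced, type II error rises from 1 − 0.900 = 10.0% to 1 − 0.875 = 12.5%. The probability of passing stage 1 and ending on exactly 27 is 2.5% at a 48% ORR and 1.0% at 28%.

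**Step 4. Evaluable number other than 69.** About 75 patients are to be enrolled. A patient counts as enrolled once dosed (Protocol 5.2.1), and measurable disease is an entry criterion (Protocol 3.1.1), so the evaluable number could approach 75. The interval rule needs 27 responders at n = 66 to 68, 28 at 69 to 71, 29 at 72 to 74 and 30 at 75. The count rule is defined only for 69. Carried unchanged to n = 75 with the stop enforced, 27 or more has alpha 0.056, and the two rules disagree at 27, 28 and 29.

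**The case against.** The strongest reply accepts the inconsistency and disputes its weight.

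- **Size and direction.** At n = 69 one count is affected, with a 2.5% chance of arising at a 48% ORR. The interval rule is the stricter one; its alpha of 0.014 respects the 0.025 limit. This is correct and stands.
- **Which rule governs.** SAP 2.1 says the SAP governs the analysis. Within it, the sections on test size and hypothesis testing both use the interval, while the count of 26 appears under sample size. That makes the interval rule the more natural reading. It does not settle the matter, because SAP 3.2.2 is also SAP text, says plainly that the null is rejected, and no precedence is stated.
- **Nature of the fault.** The stated alpha and power sit beside the count rule and are correct for it, and SAP 4.10 claims no power. The fault is indeed a conflict between sections rather than a miscalculation. The consequence remains: the test in SAP 4.10 has no stated power of its own, and the only power figure in the plan overstates it on the design's own basis.
- **Conditions on 87.5%.** The figure assumes 69 patients and an enforced stop. With the stop, power under the interval rule is 0.897 at n = 71, 0.902 at 74 and 0.890 at 75; at n = 69 without the stop it is 0.913. These conditions need stating. They do not overturn the comparison, since the stated 0.90 rests on the same two conditions and SAP 4.8 makes the stop mandatory: "If 9 or fewer patients have achieved a confirmed response (CR or PR), the study will be terminated for futility".
- **A fixed count does not travel.** Writing in a cut-off of 28 helps only at n = 69; carried to n = 75 with the stop it would have alpha 0.0375. This is a fair caution about the remedy.

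**Conclusion.** The concern holds. The two rules contradict each other at 27 of 69, neither document says which one decides, and SAP section 9 does not declare a change of test. With 69 evaluable patients and the stage 1 stop enforced, the rule in SAP 4.10 has one-sided alpha 0.0141 and power 0.875, against 0.0245 and 0.900 for the count rule. The loss is about 2.5 percentage points of power, in the conservative direction, and the disputed result is a single count. The correction is still needed before the primary analysis, because every possible result must lead to one pre-specified conclusion. The exposure would be larger if the evaluable number exceeded 69 and the count of 26 were carried forward.

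**What to change.** Name one decision rule and use it in Protocol 10.1, SAP 3.2.2 and SAP 4.10. Either of two routes works.

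1. **Keep the Clopper-Pearson rule (simplest).** State that it decides for the actual number of efficacy evaluable patients. Replace the cut-off of more than 26 with 28 or more, tied expressly to n = 69, and restate one-sided alpha as 0.014 and power as 0.875 with the futility stop enforced. Record the change of test in SAP section 9.
2. **Keep the cut-off of more than 26.** Base the decision on an exact two-stage p-value and confidence interval under stagewise ordering (p = 0.0245 at 27 of 69), and label the Clopper-Pearson interval descriptive. Alpha 0.0245 and power 0.900 then stand. This route needs a rule fixed in advance for an evaluable number other than 69, and it depends on the stop being enforced, since without it alpha is 0.0299.

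The cost is wording in the statistical sections of both documents and, on the first route, a slightly less favorable stated power. No extra patients, visits or data are needed.
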